Methods and Analysis: A quasi-experimental pilot study will be conducted to evaluate the feasibility of tattooing suspicious lymph nodes with sterile black India ink. The study will be conducted in two phases, with the second phase conditional upon the successful results of the first. In Phase I, only 10 patients who are committed to undergo upfront surgery (without neoadjuvant chemotherapy) will be included. These patients will have the suspicious lymph node tattooed by injecting India ink at the time of core needle biopsy. Intraoperatively, the axilla will be inspected to determine whether India ink tattooed in the lymph nodes can be visualized by the surgeon. Microscopic inspection for the presence of the dye in nodes retrieved by sentinel biopsy and/or axillary dissection will also be done. In Phase II, this process will be repeated for patients who undergo surgery after neoadjuvant chemotherapy.

Ethics and Dissemination: Ethical approval was obtained from the Aga Khan University Ethical Review Board (ERC# 2018-0345-1105). The process of sentinel node biopsy is a safe and routinely performed procedure at our institution. Intradermal injection of methylene blue can lead to skin necrosis; intraparenchymal injection can cause induration and erythema with associated pain. These side effects can be minimized by diluting methylene blue which will be done. The complications that can result from all additional steps of study procedures will be discussed with the patient and their full responsibility will be borne by the institution. Although sterile black India Ink is safe to administer but possible side effects can include mucosal inflammation due to spillage of the ink, abscess formation and others such as an allergic reaction. If any of these situations are encountered full responsibility to treat the side effects will be borne by the study team using departmental funds. No dissemination plan has been identified at the time of writing of this protocol.

ClinicalTrials.gov Identifier:

Keywords: *Lower Middle Income Countries, Axillary Lymph Node Dissection, Sentinel Lymph Node Biopsy, Neoadjuvant Chemotherapy, and De-Escalating Surgery, Preoperative Tattooing of the Biopsied Lymph Node, Black or India Ink*

Strengths of Study

- ✦ Robust measures will be employed as trained and credentialed surgeon, radiologists and pathologists will perform the procedures and assess the outcomes.

Limitations of Study

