of 4.2% (95% CI, 1.4 to 9.5) when the clipped node was retrieved along with sentinel lymph nodes and 10.1% when SLNs alone were retrieved without the clipped node (95% CI, 4.2 to 19.8). Furthermore, 25% of the time the clipped node was not a sentinel node and would have been missed if targeted retrieval had not been performed (8). While the study showed promising results the technique requires a sonographically visible bio-resorbable polymer (HydroMark T3) and a separate procedure for placement of radioactive iodine-125 seeds limiting application (2) (12) (13) (14) (15).

Thus, alternative methods need to be identified for marking the percutaneously biopsied lymph node at the time of core needle biopsy. One recent study that evaluated the feasibility of tattooing axillary lymph nodes with black ink before NAC identified that the black ink was visible in 93% of the patients intraoperatively, and lasted for almost 7 months in cases where lymph node retrieval was performed after NCT (14, 16). This concept is adopted based on the successful experience in gastroenterology where tattooing is widely used for marking lesions or tumors biopsied during endoscopy as the tattoo ink can remain identifiable over a long period of time (17).

There is thus a need to identify and test techniques that are practical, limit the number of procedures performed and could help limit the extent of surgery without negatively impacting outcomes. For the patient undergoing neoadjuvant chemotherapy with biopsy proven disease in the axilla, this could be achieved by developing a technique that allows marking, identification and retrieval of the biopsied lymph node, after completion of NCT at the time of SLNB. Retrieval of this previously biopsied lymph node along with SLNs, if found to be representative of the status of the remainder of the axilla, could potentially eliminate the need for routine ALND and thus limit morbidity.

To the best of our knowledge this will be the first study conducted to evaluate the feasibility of tattooing and retrieval of suspicious lymph nodes using India ink. The primary objective of our study is to evaluate whether sterile black India ink, injected percutaneously into the biopsied lymph node, can be visualized intraoperatively (Phase I). The secondary objective is to determine whether the injected India ink remains

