visible at the time of surgery even after neoadjuvant chemotherapy (lag time) and is the status of sentinel and tattooed lymph nodes predictive of the axillary nodal status.

Study Objectives

Primary Outcomes

- Intra-operative identification of tattooed lymph node(s) in upfront surgery group (Phase I)
- Intra-operative identification of tattooed lymph node(s) in the post-neoadjuvant surgery group (Phase II)

Secondary Outcome

- Concordance rate between identified sentinel node(s) and tattooed lymph node(s)

Methodology

Study Design

A quasi-experimental pilot study will be conducted to evaluate the feasibility of tattooing suspicious lymph nodes with sterile black India Ink in breast cancer patients. Patients with suspected (who have not had a breast biopsy yet but clinically are suspected to have breast cancer) or biopsy proven breast cancer, with clinically suspicious axillary nodes, who have not had axillary lymph node biopsy yet, will be considered for this study. Such patients will then undergo an ultrasound guided core needle biopsy of the breast (if not already done) as well as of the suspicious axillary lymph node, in the radiology department by study radiologists as per our current institutional protocol. For the purpose of the study, at the time of the lymph node core biopsy, the biopsied node will be tattooed by injecting 0.1-0.5 ml (larger lymph nodes will be injected with more ink) of sterile black India ink.

In the first phase, 10 patients planned for upfront surgery will be included. This part of the study will help to evaluate whether black India ink (injected percutaneously into the lymph node at the time of percutaneous axillary biopsy) can be identified intraoperatively by the surgeon and does it help in retrieval of this percutaneously biopsied lymph node. All lymph nodes excised including sentinel, tattooed (if recovered) and non-sentinel will be submitted in separately labelled containers for further

pathologic evaluation. Determination of concordance between sentinel and tattooed nodes, will be primarily done visually by the surgeon and confirmed by 2 independent pathologists, blinded to each other's findings. Pathologic evaluation will determine concordance between sentinel/tattooed and non-sentinel nodes.

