Participants as per the institutional guidelines will undergo the routine clinical breast examination by trained specialist breast surgeon and radiological investigation. Those with suspected or histologically confirmed breast cancer and suspicious (but not biopsied yet) ipsilateral axillary lymph nodes on clinical exam or ultrasound will undergo an ultrasound guided core needle biopsy of the breast as well as the single, most

suspicious axillary lymph node either concurrently with core biopsy of the breast or in addition to previously performed core needle biopsy of breast, in the radiology department by study radiologists.

The biopsied lymph nodes will be tattooed with sterile black India ink immediately following sampling of the suspicious lymph node. Those planned for upfront surgery (Phase I) will be prepared and consented for surgery. Those planned for NCT (Phase II) will receive NCT followed by definitive surgery after completion of chemotherapy.

All study patients will have a sentinel lymph node biopsy and frozen section on retrieved SLN as part of axillary surgery. For this purpose after injection of TC⁹⁹ and lymphatic mapping preoperatively, diluted methylene blue will be injected into the subareolar plexus intraoperatively. The axillary hot spot will be assessed and documented for presence or absence, using a gamma probe. Intraoperatively axilla will be inspected to determine whether sterile black India ink tattooed in the lymph nodes is visible or not. Sentinel lymph node biopsy will be performed in usual fashion including identification of palpable lymph nodes. Total number of sentinel lymph nodes retrieved, number of hot, number of blue and number of hot and blue will be documented. If the sentinel node is also the marked/tattooed node it will be assessed and documented.

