Subsequently, those with a biopsy proven axillary metastatic disease on axillary core needle biopsy (regardless of frozen section results), will proceed to have the planned breast procedure and axillary lymph node dissection levels I and II in usual fashion. Management of axilla in those participants who did not have biopsy proven metastatic disease on axillary core needle biopsy (but had a suspicious node leading to core biopsy), will be dictated by results of frozen section analysis. If the frozen section results show absence of metastatic disease in the submitted lymph nodes, no additional axillary surgery will be performed. While the frozen section is in process and results are awaited, the surgeon may proceed with the planned breast procedure. ALND will be followed by placement of a drain in the axilla as per routine. For post NCT patients, extent of fibrosis (mild, moderate or severe) will be documented. All submitted lymph nodes will be evaluated by two independent pathologists to ascertain the visualization of sterile black

India ink within the nodes, and usual histologic assessment of all submitted specimens. Correlation between, marked/tattooed and sentinel nodes (including palpable) will be determined. Tumor pathology, including type, grade, receptors (ER, PR and Her-2/neu) will be reported. Credentialed surgeon, radiologists and pathologists according to institutional guidelines will participate in the study as this will lead to minimization of experimenter/assessor bias. (Study Flow Diagram)

Statistical Analysis

Analysis will be performed in Stata version 12. Descriptive analysis will be performed. For continuous variables either Mean \pm S.D or Median with IQR will be reported depending on the normality assumption of the variables. For categorical variables frequency with percentages will be reported. Proportion of lymph node visualized intraoperatively with Black India Ink will be reported. Concordance between the sentinel lymph nodes and tattooed biopsied lymph nodes will be reported. False negative rate (FNR) will be determined to assess the findings of preoperative pathological assessment against the final histological findings of the resected nodes and 95% Confidence interval (CIs) for FNRs will be calculated by exact method for the binomial proportion.

Ethical Considerations

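### The primary outcome counts nodes seen with ink, but no step shows that a black node is the one that was biopsied

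*Combined protocol and SAP*

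**What the plan says.** The intervention concerns one node per woman. Study Procedure calls for "core needle biopsy of the breast as well as the single, most" suspicious axillary node, and Study Design states that "the biopsied node will be tattooed by injecting 0.1-0.5 ml" of ink.

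The purpose also concerns that node. Study Design asks of the ink in Phase I: "does it help in retrieval of this percutaneously biopsied lymph node". Background gives the longer-term rationale: "Retrieval of this previously biopsied lymph node along with SLNs, if found to be representative of the status of the remainder of the axilla", it might spare women routine axillary dissection.

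The outcomes are worded more loosely. Study Objectives lists "Intra-operative identification of tattooed lymph node(s) in the post-neoadjuvant surgery group (Phase II") as a primary outcome, with a parallel one for Phase I. The secondary outcome is concordance between sentinel and tattooed nodes, again with an optional plural. Under Statistical Analysis, "Proportion of lymph node visualized intraoperatively with Black India Ink will be reported". No unit, denominator or rule for several black nodes is given.

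On verification, Study Procedure says: "All submitted lymph nodes will be evaluated by two independent pathologists to ascertain the visualization of sterile black" India ink in them. Study Design adds a check that the ink can be told from methylene blue. Spread of ink beyond the injected node appears only among side effects, as "mucosal inflammation due to spillage of the ink" (Abstract, Ethics and Dissemination; similarly under Ethical Considerations).

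**The concern.** Seeing ink in a node and having recovered the biopsied node are different events. They coincide only if ink stays in the node into which it was injected. The plan measures the first and draws its value from the second. It also treats them as one: the same cited 93% is a rate of ink being visible in Background and a rate of correct identification in Sample Size Assumption.

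Suppose ink reaches a neighbouring node and the surgeon finds that node but not the biopsied one. Nothing in the plan would stop this from being recorded as a success. The error could stay hidden: women with a negative core biopsy and a negative frozen section have no further axillary surgery, so a missed biopsied node would not reach pathology. The Abstract makes Phase II conditional on successful Phase I results, and with 10 women in Phase I one misassigned case moves the rate by 10 points.

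Concordance has a related gap. If a woman has two black nodes and only one is sentinel, the plan does not say whether she is concordant.

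**Working it through.** **1. The plan's own figure.** Sample Size Assumption gives p = 0.93, 95% confidence and design effect 1, and a minimum of 100. With n = z²p(1 − p)/d² and an absolute precision of d = 0.05 (not stated, so an assumption):

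n = 1.96² × 0.93 × 0.07 / 0.05² = 100.03, or 100.

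Forty per cent of 100 is 40, which is 10 + 30. The figure reproduces, so this point does not rest on a sample-size error.

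**2. What is verified.**

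| Question | Step in the plan |
|---|---|
| Was ink seen at surgery? | Surgeon's inspection |
| Is the black material ink? | Two pathologists; comparison with methylene blue |
| Is the black node also sentinel? | Surgeon by eye, then pathologists |
| Is the black node the one biopsied? | None described |

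No clip, biopsy-site check or specimen imaging is described.

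**3. Effect on identification.** Let t be the true proportion of women whose biopsied node is found, and m the probability that some other black node is found when it is not. If any such node is scored as a success:

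reported rate = t + (1 − t)m, so excess = (1 − t)m, which is never negative.

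The documents give no value for m; 0.10 to 0.50 is an assumed range. For t, 0.93 is the plan's cited rate and 0.80 is an assumed less favourable value.

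| t | m = 0.10 | m = 0.25 | m = 0.50 |
|---|---|---|---|
| 0.80 | 0.82 (+2 points) | 0.85 (+5) | 0.90 (+10) |
| 0.93 | 0.937 (+0.7) | 0.948 (+1.8) | 0.965 (+3.5) |

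Among 30 Phase II women the expected number wrongly scored runs from 30 × 0.007 = 0.2 to 30 × 0.10 = 3. In the latter case 24/30 true retrievals would be reported as 27/30.

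**4. Effect on concordance.** Background reports that the clipped node was not sentinel 25% of the time, so c = 0.75 serves as an illustration from a different marker. Assume that a share s = 0.20 of women have one extra black node, which is sentinel with probability q.

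- Per woman, any match: c + (1 − c)sq
- Per node: (c + sq)/(1 + s)

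| q | Per woman, any match | Per node |
|---|---|---|
| 0.50 | 0.775 | 0.708 |
| 0.75 | 0.787 | 0.750 |
| 1.00 | 0.800 | 0.792 |

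Against 0.75, the first rule moves the figure up. The second moves it down, leaves it unchanged or moves it up. The direction depends on a rule that the plan does not state.

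**5. A check already within reach.** Phase I women have no chemotherapy before surgery. A core-positive biopsied node should therefore still contain tumour, unless the core removed the whole deposit. These women go on to dissection, and every submitted node has histology. A core-positive Phase I woman in whom no black node contains tumour is thus a probable misassignment. The converse fails: an inked metastatic neighbour would pass, so the check can flag a wrong node but cannot prove the right one.

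**The case against.** The strongest reply is that the plan does mean the biopsied node. Study Design says that this node is the one tattooed, and several sentences speak of the tattooed node in the singular. The optional plural may only mean nodes across women. That is fair. A reader might infer that the plan defines success as finding any black node, but no section says so; success is left undefined. What remains is that an undefined success, with no identity check, permits such scoring.

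Second, ink movement is not documented. A reader might take it as established that ink drains to neighbouring nodes during the 4 to 6 months of chemotherapy. The documents do not say this. Spillage is mentioned only as a cause of inflammation, with no rate. Spread is therefore an assumption here, and the months-long lag bears on Phase II only.

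Third, a reader might conclude that concordance is inflated. Step 4 shows that it need not be. A calculation such as 1 − 0.25² = 94% would apply only to women with two black nodes, each sentinel independently with probability 75%. Nor do all errors flatter the technique: Background values marking because the marked node is sometimes not sentinel, so higher concordance could make the tattoo look less useful.

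Fourth, Background states the primary objective as whether ink can be seen, and core-positive women have dissection regardless. Both are true and limit the consequences within this pilot. But Study Design adds retrieval of the biopsied node as a Phase I question, and a proportion seen with ink cannot answer it.

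Finally, confirmation is weakest in Phase II, where biopsy-site change may have faded and women enter whatever the core result. This stands, and is why inconclusive nodes need their own category.

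**Conclusion.** The point holds as a gap between the outcome and the purpose. The plan inks one node in order to recover it, scores nodes seen with ink, and has no step linking a black node to the biopsied one. If ink reaches a neighbour, identification is unchanged or too high, never too low. Under the assumed range of m the excess is 2 to 10 points at t = 0.80 and 0.7 to 3.5 points at t = 0.93. At the plan's cited 93% this is small beside the sampling error with 30 women (28/30 has an exact 95% interval of 77.9% to 99.2%), but more women would not remove it. It matters more if true retrieval is lower.

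For concordance the conclusion is ambiguity, not bias in a known direction. The sizes rest on assumed values; the absence of a definition and of an identity check rests on the text alone.

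**What to change.** - Define identification and concordance per woman, for the single biopsied node. Use all women inked and operated on as the denominator for identification.
- Report the number of inked nodes per woman from the planned pathology reads.
- In Phase I, flag a core-positive woman in whom no black node contains tumour as *biopsied node not confirmed*. State how many women are core-negative, since the check does not apply to them.
- In Phase II, have the planned read note any biopsy-site change in each black node, and report *cannot confirm* as its own category.
- Give both rates for all women, then again with unconfirmed women counted as not identified and with women who have more than one inked node shown separately. The second identification figure is conservative but not a strict lower bound, because an inked metastatic neighbour can pass the Phase I check.

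The cost is a few extra fields on the pathology form and a second line in the results table. No added marker, reader or procedure is needed, and care does not change. The reported rate may be less favourable, and some Phase II nodes will remain unconfirmed.

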The study will be conducted at Department of Surgery in collaboration with Department of Pathology and Radiology, the Aga Khan University Hospital Karachi-Pakistan (AKUH). AKUH is a Joint Commission International Accreditation (JCIA) accredited hospital and is one of the biggest private tertiary care hospitals in Karachi. The multidisciplinary AKUH breast surgery team consists of well qualified breast surgeons, radiologists, medical oncologists and pathologists who provide evidence based standard care to breast cancer patients following strict adherence to institutional guidelines. The reason for conducting single center study is to limit variability in management of breast cancer patients at different centers as AKUH provides a non-biased, controlled environment to evaluate the feasibility of injecting sterile black India ink and subsequently retrieval of the SLN using dual tracer technique, with attempted identification and retrieval of the marked/tattooed lymph node.

Study Participants

Women greater than 18 years old with histologically confirmed diagnosis of breast cancer or clinically suspected breast cancer and clinically suspicious ipsilateral axillary lymph nodes (on clinical exam or ultrasound) presenting to AKUH fulfilling our eligibility criteria and willing to give written informed consent for the whole duration of study period will be recruited.

Eligibility Criteria

Inclusion Criteria

- ✚ Female greater than 18 year of age

- ✦ Breast cancer patient (biopsy proven or clinically suspected) with clinically suspicious (palpable on clinical exam or abnormal by ultrasound criteria but not biopsied yet) ipsilateral axillary lymph node(s). The ultrasonographic examination will be considered suspicious for metastasis if one or more of following criteria are present: 1. Eccentric cortical enlargement (>3 mm) or lobulation with displacement of hilum 2. Absent hilum and irregular border and hypoechoic echotexture 3. Spherical node 4. Perinodal vascularity. (18-20)
- ✦ Participants willing to undergo axillary lymph node percutaneous biopsy with marking/tattooing of the biopsied lymph node at Aga Khan University Hospital
- ✦ Participants intending to have definitive surgery at Aga Khan University Hospital

Exclusion Criteria

- ✦ Participants with terminal disease like renal failure will be excluded because these conditions can have profound effect on their course of treatment
- ✦ Participants with distant metastases

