- ✦ Participants with prior breast or axillary surgery
- ✦ Participants with bilateral breast cancer, and those who have already had an axillary core needle biopsy prior to inclusion (to avoid a second procedure for tattooing)
- ✦ Participants with recurrent breast malignancy because their course of treatment might be different
- ✦ Participants that were initially suspected to have breast cancer, but pathology results did not confirm the diagnosis
- ✦ Pregnant and lactating women
- ✦ Men with breast cancer

Sampling Strategy

The study participants will be recruited through purposive sampling technique from a population of female patients, presenting to AKUH with biopsy proven or suspected breast cancer with a clinically suspicious lymph node in the ipsilateral axilla.

Sample Size Assumption

The sample size assumptions were based on reported proportion of correctly identified marked/tattooed lymph of 93% (14), with confidence level of 95% and design effect of 1, the minimum sample size calculated is 100 breast cancer patients. Since we are conducting a small feasibility pilot study, it will be conducted on 40% of the calculated sample size, i.e. on 40 breast cancer patients with clinically suspicious, percutaneously biopsied and tattooed ipsilateral axillary lymph node. The sample size was calculated through Open-EPI version 3.01.

The first 10 participants will be those with clinically suspicious nodes having undergone a core needle biopsy with simultaneous injection of India Ink and now planned for upfront surgery. The next 30 patients enrolled will be those who are planned for NCT, regardless of the pathologic results of the axillary core needle biopsy. Since surgery in these 30 patients will be deferred for approximately 6 months, it will allow us to know if delayed retrieval of the tattooed lymph node is possible after NCT.

Study Procedure

Female patients with histologically confirmed diagnosis of breast cancer or clinically suspected breast cancer with clinically suspicious ipsilateral lymph nodes (not biopsied yet) will be approached to participate in our study by the research team. Consent from patients will be obtained by those who meet the inclusion criteria and intend to have surgical treatment at AKUH.

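### Purposive enrolment with no screening log leaves both primary identification proportions open to patient selection that a confidence interval would not show

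*Combined protocol and SAP*

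**What the plan says.** Sampling Strategy: "The study participants will be recruited through purposive sampling technique from a population of female patients". The sentence goes on to describe that population as women attending the hospital with proven or suspected breast cancer and a suspicious node on the same side.

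Study Procedure: women with that profile "will be approached to participate in our study by the research team". It does not say that all of them will be approached, or in what order.

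Eligibility Criteria: a node qualifies if it is "palpable on clinical exam or abnormal by ultrasound criteria but not biopsied yet". The ultrasound criteria are listed. No overall size, depth or accessibility limit is set.

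Study Procedure also fixes the node within a woman. The radiologist performs a "core needle biopsy of the breast as well as the single, most" suspicious axillary node, and "The biopsied lymph nodes will be tattooed with sterile black India ink immediately following sampling of the suspicious lymph node".

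Study Objectives lists two primary outcomes: intraoperative identification of the tattooed node in the upfront-surgery group (Phase I) and in the post-neoadjuvant group (Phase II). Statistical Analysis treats them descriptively: "Proportion of lymph node visualized intraoperatively with Black India Ink will be reported". An exact binomial interval is specified for the false negative rate only.

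Limitations of Study names the single institution, the small sample and the restriction to women. It does not name patient selection.

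**The concern.** A purposive sample is one in which the investigators choose whom to include. Eligibility rests on examination or ultrasound, so the features of the node can be known before a woman is approached. The Study Design section scales the ink volume to node size, so the plan itself expects nodes to vary. If visibility varies with such features, and women with easier nodes are approached more readily, the enrolled group will do better than the eligible population.

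Neither phase has a comparator in which this effect would cancel. Phase II also depends on successful Phase I results, and with 10 women each one moves the Phase I proportion by 1/10 = 10 percentage points. Without a record of who was eligible but not enrolled, neither the team nor a reader could judge afterwards how representative the proportion is.

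**Working it through.** **1. The plan's own figure.** Sample Size Assumption gives an expected proportion of 93%, 95% confidence, design effect 1 and n = 100. The half-width d is not stated. With n = z²p(1−p)/d², z = 1.96, p = 0.93 and d = 0.05 (an assumption):

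n = 3.8415 × 0.93 × 0.07 / 0.0025 = 100.03.

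So the 100 reproduces if d = 0.05, and 40% of it gives the 40 women to be enrolled. Consecutive enrolment changes neither number.

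**2. Where selection can enter.**

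- *Which node within a woman:* fixed as the single most suspicious one, and tattooed straight after sampling. No room for choice.
- *Which phase:* set by clinical stage, the surgeon's evaluation and the patient's preference (Study Design).
- *Which eligible women are approached:* purposive, with no order, no requirement to approach all, and no log. This is the open route.

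**3. How a selection effect would act.** Let s be the share of eligible women with easy nodes, q the share among those enrolled, and E and H the visualisation rates in easy and hard nodes. Then

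bias = (q − s) × (E − H).

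None of these four quantities is in the document. The values below are illustrations only, with s = 0.5.

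| E, H | q = 0.8 | q = 1.0 (only easy nodes enrolled) |
|---|---|---|
| 97%, 90% | 0.3 × 0.07 = +2.1 points | 0.5 × 0.07 = +3.5 points |
| 95%, 80% | 0.3 × 0.15 = +4.5 points | 0.5 × 0.15 = +7.5 points |
| 95%, 65% | 0.3 × 0.30 = +9.0 points | 0.5 × 0.30 = +15 points |
| 93%, 93% | 0 | 0 |

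If hard nodes were over-represented (q < s), the sign would reverse.

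**4. Comparison with sampling error.** At p = 0.93 the normal-approximation half-width is 1.96 × √(0.0651/n):

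- n = 10: 15.8 points
- n = 30: 9.1 points

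The exact 95% interval would be 55.5% to 99.7% for 9/10 and 77.9% to 99.2% for 28/30. Most of the illustrated biases are smaller than the sampling error of either phase. Only the most extreme (+15) exceeds the Phase II half-width. The two differ in kind, however: an interval displays sampling error, but it is centred on the selected group's rate and carries no sign of selection.

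**The case against.** The case on the other side has real force.

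- *The benign reading.* The stated purpose of the sampling may be no more than the disease profile in the rest of the sentence. Study Participants says that women who meet the criteria and consent will be recruited. Nothing mentions size, depth or ease of injection as grounds for choosing anyone. This stands: the document shows no intention to select easy cases. But it does not exclude selection either, and the eligibility list already does the work that the benign reading gives to the word purposive.
- *Choosing nodes.* A reader might infer that the team can pick convenient nodes to inject. The document contradicts this, because the node within each woman is fixed.
- *One team doing everything.* A reader might infer that the same people select, inject and judge. In fact study radiologists inject, the surgeon judges visibility, and two pathologists blinded to each other's findings examine the nodes. That separation limits assessor bias. It does not govern who is approached.
- *The sample-size assumptions.* A reader might take "with confidence level of 95% and design effect of 1" as a promise of random or consecutive sampling. A design effect of 1 only means no inflation for clustering, so there is no contradiction to find there.
- *A known size of bias.* A reader might set a bias range against a 5-point margin behind n = 100. The margin is back-solved, not stated, and the study enrols 10 and 30 women, not 100. No such comparison is supported.
- *A pilot.* Non-consecutive sampling is a recognised choice in a descriptive, single-centre feasibility study that admits limited generalizability. This lowers the weight of the point but does not remove it, since patient selection is not among the limitations listed.

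**Conclusion.** The concern holds at the level of patients, not nodes. The plan specifies purposive sampling and provides neither consecutive enrolment nor a record of eligible women left out. Both primary proportions are uncontrolled, so selection of whom to approach could bias them, plausibly upward.

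This conclusion rests on two conditions that the document leaves open: that visibility depends on node features, and that these features influence who is approached. If either fails, the bias is zero. Its size therefore cannot be derived, and the 0 to 15 points shown are illustrative only. The effect on the decision to open Phase II cannot be assessed either, because no success threshold is stated. The weakness concerns design and reporting; no stated figure is wrong. It is worth acting on because the remedy is better than the stated method and costs very little.

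**What to change.** In Sampling Strategy, replace the purposive technique with consecutive enrolment within each phase. Every eligible woman planned for upfront surgery is approached in order of presentation until 10 are enrolled; then every eligible woman planned for neoadjuvant chemotherapy is approached in order of presentation until 30 are enrolled. The rule has to run within phase because the eligibility criteria do not include the treatment plan, so a single consecutive series would conflict with the sequence of 10 and then 30.

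Keep a screening log with these steps: eligible, approached, consented, tattooed, reached surgery, and the reason wherever a woman stops. Report it with each primary proportion. The last two steps matter because Sample Size Assumption describes the first 10 as already injected and by then planned for upfront surgery. Group membership may thus be settled after tattooing, and the document does not say how tattooed women who do not reach surgery, or whose plan changes, are counted.

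Cost: a short rewording, one form and a little coordinator time. Sample size and clinical procedures are unchanged. Label: cheap improvement.
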